7.1.6.3.2 Follow-up Visits

Subjects who discontinue trial treatment for reasons other than disease progression will move into the Follow-up Phase and should be assessed Q6W by radiologic imaging to monitor disease status. Every effort should be made to collect information regarding disease status until the start of new anti-cancer therapy, disease progression, death, end of trial [or if the subject begins retreatment with pembrolizumab as detailed in [Section 7.1.4.5]. Information regarding post-trial anticancer treatment will be collected if new treatment is initiated.

Subjects who are eligible to receive retreatment with pembrolizumab according to the criteria in Section 7.1.4.5 will move from the Follow-up Phase to the Second Course Phase when they experience disease progression. Details are provided in the Trial Flow Chart (Section 6) for retreatment with pembrolizumab.

Protocol/Amendment No.: 394-06

7.1.6.3.3 Survival Follow-up

Subjects who experience confirmed disease progression or start a new anti-cancer therapy, will move into the Survival Follow-Up Phase and should be contacted by telephone approximately every 12 weeks to assess for survival status until death, withdrawal of consent, or the end of the trial, whichever occurs first.

- For patients who discontinue treatment due to PD
 - Date of the first survival follow-up contact should be 12 weeks from the date of the 30 day safety FU Visit
 - o Note: if a subject does not have a 30-day safety follow up visit the date is calculated from the discontinuation visit.
- For subjects who discontinue treatment for reasons other than PD
 - o Undergo a 30-day safety follow-up visit and continue with imaging follow-up
 - o The date of the first survival follow-up contact should be based either on the date that the subject has first radiologic evidence of progressive disease, or on the date the subject starts a new anti-cancer therapy.

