5.2.1.2 Dose Modification (Escalation/Titration/Other)

5.2.1.2.1 Immune-Related Events and Dose Modification (Withhold, Treat, Discontinue)

Dose Modification and Toxicity Management for Non-hepatic Immune-related AEs Associated with Pembrolizumab

AEs associated with pembrolizumab exposure may represent an immune-related response. These irAEs may occur shortly after the first dose or several months after the last dose of pembrolizumab treatment and may affect more than one body system simultaneously. Therefore, early recognition and initiation of treatment is critical to reduce complications. Based on existing clinical study data, most irAEs were reversible and could be managed with interruptions of pembrolizumab, administration of corticosteroids and/or other supportive care. For suspected irAEs, ensure adequate evaluation to confirm etiology or exclude other causes. Additional procedures or tests such as bronchoscopy, endoscopy, skin biopsy may be included as part of the evaluation. Based on the severity of irAEs, withhold or permanently discontinue pembrolizumab and administer corticosteroids.

Dose Modification and Toxicity Management Guidelines for Non-hepatic irAEs associated with pembrolizumab monotherapy, coformulations, or IO combinations are provided in Table 3.

Protocol/Amendment No.: 394-06

Table 3 Dose Modification and Toxicity Management Guidelines for Non-hepatic Immune-related Adverse Events Associated with Pembrolizumab Monotherapy, Coformulations or IO Combinations

General instructions:

- 1. Severe and life-threatening irAEs should be treated with IV corticosteroids followed by oral steroids. Other immunosuppressive treatment should begin if the irAEs are not controlled by corticosteroids.
- 2. Pembrolizumab monotherapy, coformulations or IO combinations must be permanently discontinued if the irAE does not resolve or the corticosteroid dose is not ≤10 mg/day within 12 weeks of the last treatment.
- 3. The corticosteroid taper should begin when the irAE is \leq Grade 1 and continue at least 4 weeks.
- 4. If pembrolizumab monotherapy, coformulations or IO combinations have been withheld, treatment may resume after the irAE decreased to ≤ Grade 1 after corticosteroid taper.

irAEs	Toxicity Grade (CTCAEv4.0)	Action With Pembrolizumab Monotherapy, Coformulations or IO Combinations	Corticosteroid and/or Other Therapies	Monitoring and Follow-up

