6.0 TRIAL FLOW CHART

6.1 Initial Treatment with Study Drug

Trial Period:	Screening Phase		Treatment Cycles (3-Week Cycles) End of Treatment Treatment									t	
Treatment Cycle/Title:	Screening	1	2	3	4	5	6	7	≥8	Discon	Safety Follow-up	Follow-Up Visits	Survival Follow- Up ^a
										At time of discon	30 days post last dose	Every 6 weeks post-discon	Every 12 weeks
Scheduling Window (Days) ^b	-28 to -1		±3	±3	±3	±3	±3	±3	±3	±3	±7	±7	±7
Administrative Procedures			_	 	-	_	_	_	_	-			
Informed consent	X												
Informed consent for future biomedical research (optional)	X												
Inclusion/exclusion criteria	X												
Subject identification card	X												
Demographics and medical history	X												
Prior and concomitant medication review	X	X	X	X	X	X	X	X	X	X	X		
Post-study anticancer therapy status											X	X	X
Survival status ^a		<										>	X
Clinical Procedures/Assessments													
Review adverse events c	X	X	X	X	X	X	X	X	X	X	X	X	
Full physical examination	X									X			
Directed physical examination		X	X	X	X	X	X	X	X		X		
Child-Pugh Score d	X												

Protocol/Amendment No.: 394-06

Trial Period:	Screening Phase	Treatment Cycles (3-Week Cycles) End of Treatment Treatment										Post-treatmen	t
Treatment Cycle/Title:	Screening	1	2	3	4	5	6	7	≥8	Discon	Safety Follow-up	Follow-Up Visits	Survival Follow- Up ^a
										At time of discon	30 days post last dose	Every 6 weeks post-discon	Every 12 weeks
Scheduling Window (Days) ^b	-28 to -1		±3	±3	±3	±3	±3	±3	±3	±3	±7	±7	±7
Height ^q , weight, and vital signs (T, P, RR, BP)	X	X	X	X	X	X	X	X	X	X			
12-Lead electrocardiogram	X												
ECOG performance status e	X	X	X	X	X	X	X	X	X	X			
EQ-5D, EORTC QLQ-C30 ^f		X	X	X	X	X		X	X	X	X		
Pembrolizumab/placebo administration		X	X	X	X	X	X	X	X				
LOCAL Laboratory Assessments ⁿ													
Pregnancy test g	X												
PT/INR h	Xe		X	X	X	X	X	X	X	X	X		
CBC with differential ^h	Xe		X	X	X	X	X	X	X	X	X		
Chemistry panel and liver panel ^h	Xe		X	X	X	X	X	X	X	X	X		
Urinalysis ⁱ	X		X		X		X		X	X			
T3, FT4, and TSH ^{i,J}	X		X		X		X		X	X	X		
AFP ^{jk}	Xe		X	X	X	X	X	X	X	X	X		
Anti-HCV antibody ¹	X												

Protocol/Amendment No.: 394-06

Trial Period:	Screening Phase									End of Treatment	Post-treatment			
Treatment Cycle/Title:	Screening	1	2	3	4	5	6	7	≥8	Discon	Safety Follow-up	Follow-Up Visits	Survival Follow- Up ^a	
										At time of discon	30 days post last dose	Every 6 weeks post-discon	Every 12 weeks	

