7.1.1.6 Subsequent Anti-Cancer Status

The investigator or qualified designee will review all new anti-cancer therapy initiated after the last dose of trial treatment. If a subject initiates a new anti-cancer therapy within 30 days after the last dose of trial treatment, the 30 day Safety Follow-up visit must occur before the first dose of the new therapy.

Once new anti-cancer therapy has been initiated the subject will move into survival follow-up. Details regarding survival status follow-up are outlined in 7.1.6.3.3 – Survival Follow Up.

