7.1.6.3 Post-Treatment Visits

7.1.6.3.1 Safety Follow-up Visits

The mandatory Safety Follow-up Visit should be conducted approximately 30 days after the last dose of trial treatment or before the initiation of a new anti-cancer treatment, whichever comes first.

All AEs that occur prior to the Safety Follow-Up Visit should be recorded. Subjects with an AE of Grade >1 will be followed until the resolution of the AE to Grade 0-1 or until the beginning of a new anti-cancer therapy, whichever occurs first. SAEs that occur within 90 days of the end of or within 30 days of the end of treatment if the subject initiates new anticancer therapy, whichever is earlier should also be followed and recorded.

Subjects who are eligible for retreatment may have up to two safety follow-up visits, one after the Initial Treatment Period and one after the Second Course Treatment Phase.

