7.2.3 Immediate Reporting of Adverse Events to the Sponsor

7.2.3.1 Serious Adverse Events

An serious adverse event is any adverse event occurring at any dose or during any use of Sponsor's product that:

- Results in death;
- Is life threatening;
- Results in persistent or significant disability/incapacity;
- Results in or prolongs an existing inpatient hospitalization;
- Is a congenital anomaly/birth defect;
- Is an other important medical event.

Note: In addition to the above criteria, adverse events meeting either of the below criteria, although not serious per ICH definition, are reportable to the Sponsor in the same timeframe

MK-3475-394-06 Final Protocol 03-Nov-2022 Confidential

Protocol/Amendment No.: 394-06

as SAEs to meet certain local requirements. Therefore, these events are considered serious by the Sponsor for collection purposes.

• Is a new cancer (that is not a condition of the study);

• Is associated with an overdose.

Refer to Table 7 for additional details regarding each of the above criteria.

For the time period beginning when the consent form is signed until treatment allocation/randomization, any serious adverse event, or follow up to a serious adverse event, including death due to any cause other than progression of the cancer under study (refer to [Section 7.2.3.3] for additional details), that occurs to any subject must be reported within 24 hours to the Sponsor if it causes the subject to be excluded from the trial, or is the result of a protocol-specified intervention, including but not limited to washout or discontinuation of usual therapy, diet, placebo treatment or a procedure.

For the time period beginning at treatment randomization through 90 days following cessation of trial treatment, or 30 days following cessation of trial treatment if the subject initiates new anticancer therapy, whichever is earlier, any serious adverse event, or follow up to a serious adverse event, including death due to any cause, other than progression of the cancer under study (reference Section 7.2.3.3 for additional details) whether or not related to the Sponsor's product, must be reported within 24 hours to the Sponsor either by electronic media or paper. Electronic reporting procedures can be found in the EDC data entry guidelines. Paper reporting procedures can be found in the Investigator Trial File Binder (or equivalent).

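### After stopping for progression, a subject off new therapy has no scheduled adverse event review between about day 30 and the end of the 90-day SAE window

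*Protocol*

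**What the plan says.** - **Collection duty.** Protocol Section 7.2.3.1 starts the SAE reporting period at randomization and gives its end as follows: "through 90 days following cessation of trial treatment, or 30 days following cessation of trial treatment if the subject initiates new anticancer therapy". The shorter of the two periods applies. Section 4.2.3.4 sets the same period for hospitalizations and emergency room visits.
- **Last scheduled safety contact.** Section 7.1.6.3.1: "The mandatory Safety Follow-up Visit should be conducted approximately 30 days after the last dose of trial treatment". The flow chart allows ±7 days.
- **After stopping for progression.** Section 7.1.6.3.3: "Date of the first survival follow-up contact should be 12 weeks from the date of the 30 day safety FU Visit". If there was no 30-day visit, the 12 weeks run from the discontinuation visit. The stated purpose of the call is survival status. Section 7.1.4.4 requires no imaging after the end-of-treatment scan in these subjects.
- **After stopping for another reason.** Section 7.1.6.3.2: "Subjects who discontinue trial treatment for reasons other than disease progression will move into the Follow-up Phase", with assessments every 6 weeks until progression, new therapy, death or the end of the trial.
- **Flow charts.** In Section 6.1 the row "Review adverse events c" (the final letter is a footnote mark) is marked through the Follow-Up Visits column and is blank under Survival Follow-Up. The second-course chart in Section 6.2 is also blank there.
- **Late events.** Section 5.2.1.2.1: "These irAEs may occur shortly after the first dose or several months after the last dose of pembrolizumab treatment".

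**The concern.** The collection period and the contact schedule do not match for one group: subjects who stop for progression and have not started new anticancer therapy. Their SAE window stays open to day 90, but after the safety visit nobody is scheduled to ask them about adverse events.

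The protocol itself expects immune-related events months after the last dose. A serious hepatitis or pneumonitis that first appears in days 31 to 90 is recorded only if the site learns of it some other way. Because the other discontinuation route does include adverse event review in that period, the chance of recording such an event depends on why treatment stopped. That affects how the late SAE data can be read, both in the final safety tables and by the eDMC.

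**Working it through.** The documents state no figure to reproduce. The check is a day count, taking the last dose as day 0 and as the date treatment ceased.

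**Inputs:** SAE window 90 days (Section 7.2.3.1); safety visit at about day 30, ±7 (Sections 7.1.6.3.1 and 6.1); first survival call 12 weeks later (Section 7.1.6.3.3), ±7 (Section 6.1); follow-up visits every 6 weeks, ±7 (Section 6.1).

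**1. Stopped for progression, 30-day visit held**
- Nominal call: 30 + 12 × 7 = day 114, which is 114 − 90 = 24 days after the window closes.
- Earliest: (30 − 7) + (84 − 7) = day 100. Latest: (30 + 7) + (84 + 7) = day 128.
- Part of the window without scheduled contact: (90 − 30) / 90 = 60/90 = 67%.

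**2. Stopped for progression, no 30-day visit (fallback rule)**
- Discontinuation visit at day 0: 0 + 84 = day 84, inside the window.
- Discontinuation visit at day 6: 6 + 84 = day 90, the last day of the window.
- Discontinuation visit at day 21 (one cycle after the last dose): 21 + 84 = day 105, outside it.
- In every case the call has no adverse event review marked.

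**3. Stopped for another reason, progression-free and off new therapy**

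| Discontinuation visit | First 6-weekly visit | Second 6-weekly visit | Nominal visits by day 90 |
|---|---|---|---|
| Day 0 | Day 42 (35–49) | Day 84 (77–91) | 2 |
| Day 21 | Day 63 (56–70) | Day 105 (98–112) | 1 |

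Adverse event review is marked at these visits.

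**4. Other contacts in days 31 to 90 after progression.** The 6-weekly visits are restricted to the other route, and imaging has ended. No scheduled contact remains.

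**5. Subjects affected.** The documents do not give the share who stop for progression. If it were 60% to 80% (an assumption), 0.60 × 450 = 270 to 0.80 × 450 = 360 subjects would enter this route. That is a ceiling on subjects, not a count of missed SAEs. Those who start new therapy have a 30-day window and drop out of it, as do early deaths, and neither number is given.

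**The case against.** The strongest reply is that the reporting duty is explicit and several provisions work alongside it:

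- SAEs that the investigator judges related and learns of are reportable at any time (Section 7.2.3.1).
- Adverse events above Grade 1 are followed to Grade 0–1 or new therapy (Section 7.1.6.3.1).
- Unresolved drug-related laboratory abnormalities are followed to resolution (Section 7.1.3.1).
- Footnote c of the Section 6.1 chart has hepatic events of clinical interest collected throughout the study. Section 7.2.3.2 sets 14 days for such events, so these two also need reconciling.
- The sponsor may request survival updates at any time (Section 7.1.6.3.4).

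These stand as partial safeguards and narrow the gap to new-onset SAEs. None is a scheduled search for them: the first depends on the site being told, the next two follow events already known, footnote c adds no contact, and the last is optional and concerns survival.

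Section 5.8.1 also tells discontinued subjects to complete the flow-chart visits. But Sections 7.1.6.3.2 and 7.1.6.3.3 assign subjects to a route by reason for stopping, so this does not clearly put progressed subjects on the 6-weekly schedule.

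The contrast between routes is also limited. The 6-weekly visits end at progression or new therapy. The design assumes median PFS of 1.5 months on control and a hazard ratio of 0.65, so 1.5 / 0.65 = about 2.3 months on pembrolizumab, measured from randomization. Many subjects could leave that schedule early.

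A reader might infer three stronger things that the documents do not support:

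- *The first call always falls after day 90.* The fallback rule can put it at day 84.
- *Progressed subjects are never asked about adverse events.* They are, at discontinuation and at the safety visit.
- *The SAE comparison between arms is biased.* The documents give no reasons for stopping by arm and no late SAE rate. If placebo subjects stopped for progression more often, under-detection would fall more on placebo and would not hide pembrolizumab toxicity.

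**Conclusion.** The mismatch is real and should be corrected. For subjects who stop for progression and do not start new therapy, days 31 to 90 (60 of 90 days, 67%) contain no scheduled adverse event review. Where the 30-day visit is held within its window, they contain no scheduled contact at all. The first call then comes at about day 114 (100 to 128); under the fallback rule it comes at about day 84 to 105. No adverse event review is attached to it in either case.

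New-onset SAEs in that period can be missed, and their detection depends on the reason for stopping. Detection could therefore differ by arm, but neither the size nor the direction can be computed from the documents. The conclusion rests on the routing in Sections 7.1.6.3.2 and 7.1.6.3.3 being followed as written. The EDC data entry guidelines were not available and may contain a prompt for SAEs.

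**What to change.** In Section 7.1.6.3.3, time the first survival contact from the last dose, at day 90 (+7 days), and continue every 12 weeks after that. Apply this to every subject who is in survival follow-up by then and whose 90-day window is still open, including those with no 30-day visit. In the charts of Sections 6.1 and 6.2, mark adverse event review for that contact, limited to SAEs and hospitalizations, so that the charts agree with Sections 4.2.3.4, 7.1.6.3.1, 7.1.6.3.3 and 7.2.3.1.

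The cost is small. In the usual case an existing call moves 114 − 90 = 24 days earlier, about 3 weeks, and becomes slightly longer. Protocol and CRF wording change, with no new visit or procedure.

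An optional, secondary addition concerns subjects who switch therapy before day 30. Section 7.1.1.6 says that "the 30 day Safety Follow-up visit must occur before the first dose of the new therapy", while collection still runs to day 30. One call at day 30 would cover the remainder, at the cost of one extra contact for those subjects.

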7.1.6.3.4 Survival Status

To ensure current and complete survival data is available at the time of database locks, updated survival status may be requested during the course of the study by the Sponsor. For example, updated survival status may be requested prior to but not limited to an external Data Monitoring Committee (eDMC) review, interim and/or final analysis. Upon Sponsor notification, all subjects who do not/will not have a scheduled study visit or study contact during the Sponsor defined time period, will be contacted for their survival status (excluding subjects that have a previously recorded death event in the collection tool).

7.2 Assessing and Recording Adverse Events

An adverse event is defined as any untoward medical occurrence in a patient or clinical investigation subject administered a pharmaceutical product and which does not necessarily have to have a causal relationship with this treatment. An adverse event can therefore be any unfavourable and unintended sign (including an abnormal laboratory finding, for example), symptom, or disease temporally associated with the use of a medicinal product or protocol-specified procedure, whether or not considered related to the medicinal product or protocol-specified procedure. Any worsening (i.e., any clinically significant adverse change in frequency and/or intensity) of a preexisting condition that is temporally associated with the use of the Sponsor's product, is also an adverse event.

Changes resulting from normal growth and development that do not vary significantly in frequency or severity from expected levels are not to be considered adverse events.

Protocol/Amendment No.: 394-06

Examples of this may include, but are not limited to, teething, typical crying in infants and children and onset of menses or menopause occurring at a physiologically appropriate time.

Sponsor's product includes any pharmaceutical product, biological product, device, diagnostic agent or protocol-specified procedure, whether investigational (including placebo or active comparator medication) or marketed, manufactured by, licensed by, provided by or distributed by the Sponsor for human use.

Adverse events may occur during clinical trials, or as prescribed in clinical practice, from overdose (whether accidental or intentional), from abuse and from withdrawal.

Progression of the cancer under study is not considered an adverse event.

All adverse events that occur after the consent form is signed but before treatment allocation/randomization must be reported by the investigator if they cause the subject to be excluded from the trial, or are the result of a protocol-specified intervention, including but not limited to washout or discontinuation of usual therapy, diet, placebo treatment or a procedure. From the time of treatment allocation/randomization through 30 days following cessation of treatment, all adverse events must be reported by the investigator. Such events will be recorded at each examination on the Adverse Event case report forms/worksheets. The reporting timeframe for adverse events meeting any serious criteria is described in section 7.2.3.1. The investigator will make every attempt to follow all subjects with nonserious adverse events for outcome.

Electronic reporting procedures can be found in the Electronic Data Capture (EDC) data entry guidelines. Paper reporting procedures can be found in the Investigator Trial File Binder (or equivalent).

7.2.1 Definition of an Overdose for This Protocol and Reporting of Overdose to the **Sponsor**

In this trial, an overdose is any dose higher than ≥1000 mg (5 times the protocol defined dose) of pembrolizumab. No specific information is available on the treatment of over dose of pembrolizumab. In the event of overdose, study treatment should be discontinued and the subject should be observed closely for signs of toxicity. Appropriate supportive treatment should be provided if clinically indicated.

If an adverse event(s) is associated with ("results from") the overdose of Sponsor's product or vaccine, the adverse event(s) is reported as a serious adverse event, even if no other seriousness criteria are met.

If a dose of Sponsor's product or vaccine meeting the protocol definition of overdose is taken without any associated clinical symptoms or abnormal laboratory results, the overdose is reported as a non-serious Event of Clinical Interest (ECI), using the terminology "accidental or intentional overdose without adverse effect."

All reports of overdose with and without an adverse event must be reported by the investigator within 24 hours to the Sponsor either by electronic media or paper. Electronic

MK-3475-394-06 Final Protocol 03-Nov-2022 Confidential

085/RXM

Protocol/Amendment No.: 394-06

reporting procedures can be found in the EDC data entry guidelines. Paper reporting procedures can be found in the Investigator Trial File Binder (or equivalent).

